10.2 Definition of analysis sets

The full analysis set (FAS): all randomised subjects. Subjects will be analysed “as randomised”.

The safety analysis set (SAS): all randomised subjects exposed to at least one dose of randomised treatment. Subjects will be analysed “as treated”.

The per protocol analysis set (PP): subjects from the FAS who have not violated any inclusion/exclusion criteria and have used the randomised treatment for at least 47 weeks (for subjects receiving somapacitan) or 329 days (for subjects receiving Norditropin[®]) corresponding to 90% of the planned exposure, during the main trial period. Subjects will be analysed “as treated”.

Exclusion of data from analyses should be used restrictively, and normally no data should be excluded from the FAS. The subjects or observations to be excluded, and the reasons for their exclusion must be documented before interim database lock for the main trial (52 weeks of treatment). The subjects and observations excluded from analysis sets, and the reason for this, will be described in the CTR. Three observation periods are defined,

- on-treatment: from first administration and up until last trial contact, visit 7 or 14 days after last administration, whichever comes first
- in-trial without use of ancillary therapy: from first administration and up until last trial contact, visit 7 or first use of ancillary therapy, whichever comes first
- in-trial: from first administration and up until visit 7 or last trial contact, whichever comes first

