4.3.2.4 Safety

Endpoint title	Time frame	Unit
Change in fasting plasma glucose	From screening (visit 1) to visit 7 (week 52) From screening (visit 1) to visit 11 (week 104) From screening (visit 1) to visit 15 (week 156) From screening (visit 1) to visit 19 (week 208)	mmol/L
Change in homeostatic model assessment (HOMA)	From screening (visit 1) to visit 7 (week 52) From screening (visit 1) to visit 11 (week 104) From screening (visit 1) to visit 15 (week 156) From screening (visit 1) to visit 19 (week 208)	%
Change in Glycated haemoglobin (HbA1c)	From screening (visit 1) to visit 7 (week 52) From screening (visit 1) to visit 11 (week 104)	% point

	From screening (visit 1) to visit 15 (week 156) From screening (visit 1) to visit 19 (week 208)	
--	--	--

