9.1.5 Patient reported outcome questionnaires

PRO questionnaires will be completed by the parent/LAR. The PROs should preferably be completed by the same parent/LAR.

- G-DAT
- TB-CGHD-O
- TB-CGHD-P
- TRIM-CGHD-O (only in countries were available)

For subjects who have changed treatment from Norditropin® to somapacitan at week 52.

- Growth hormone PPQ will be completed in the diary at week 56.

For Estonia, Hungary, Ireland, Latvia, Norway, Poland, Serbia, Spain: See [Appendix 9](#)

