10.3.3 Exploratory endpoints

The exploratory endpoints will be analysed based on the ‘on-treatment’ observation period. TB-CGHD-O and TB-CGHD-P scores will be analysed using a MMRM with an unstructured covariance matrix on all relevant post-baseline values as dependant variables. The model will include treatment, gender, age group, region, GH peak group and gender by age group by region interaction term as factors, all nested within week as a factor. From the MMRM, the treatment differences will be estimated and the corresponding 95% CI and p-values will be reported for week 26 and week 52, respectively. Changes from baseline to week 26 and week 52 in TRIM-CGHD-O scores will be analysed using a MMRM with an unstructured covariance matrix. The model will include treatment, gender, age group, region, GH peak group and gender by age group by region interaction term as factors and baseline value as a covariate, all nested within week as a factor. From the MMRM, the treatment differences will be estimated and the corresponding 95% CI and p-values will be reported for week 26 and week 52, respectively. G-DAT and PPQ data will be analysed using descriptive statistics.

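### The week-56 preference questionnaire (PPQ) is assigned to an on-treatment period that ends at visit 7, so its planned analysis would contain no on-schedule responses

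*Combined protocol and SAP*

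**What the plan says.** Section 10.2 introduces the periods with "Three observation periods are defined". The on-treatment period is given as "on-treatment: from first administration and up until last trial contact, visit 7 or 14 days after last administration, whichever comes first". The period without ancillary therapy runs "from first administration and up until last trial contact, visit 7 or first use of ancillary therapy, whichever comes first". The third is "in-trial: from first administration and up until visit 7 or last trial contact, whichever comes first". Visit 7 is one of the competing end points in all three.

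Section 10.3.3 then states: "The exploratory endpoints will be analysed based on the ‘on-treatment’ observation period". The same paragraph plans descriptive statistics for the PPQ and makes no exception for it. Section 4.3.3 lists the PPQ as an exploratory endpoint for children who switch from Norditropin to somapacitan. Section 9.1.5 gives its timing: "Growth hormone PPQ will be completed in the diary at week 56". Flowchart note e places the switch at visit 7.

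Sections 4.3.2.4 and 4.3.2.5 name three safety endpoints (fasting plasma glucose, HOMA, HbA1c) and two pharmacodynamic endpoints (IGF-I SDS, IGFBP-3 SDS). Each has a week-52 time frame and three later ones, for example "From screening (visit 1) to visit 11 (week 104"). Section 10.3.2 lists only the change to week 52 for these five. Section 10.3.5 says that adverse event tables like those for the main phase will be made for the extension, without defining the extension as an observation period.

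**The concern.** An endpoint that exists only after visit 7 is tied to a period that cannot extend beyond visit 7. Following Sections 10.2 and 10.3.3 as written gives an empty PPQ table. An analyst who fills the table has departed from the stated rule and must choose a replacement, for instance whether a child who stopped somapacitan shortly after the switch still counts.

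The same missing text leaves a gap further on. Section 5.1 says the three-year extension is there to evaluate safety, yet its laboratory safety and pharmacodynamic endpoints have neither an observation period nor a stated analysis. Under Section 10.3.4 the sponsor becomes unblinded to the main-phase allocation at the interim lock, so rules for the extension that are still open then would be set with knowledge of the main-phase results.

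**Working it through.** The plan gives no figure to reproduce here. The check compares dates and reads the sections against each other.

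**1. Latest end of the on-treatment period.** The flowchart puts visit 7 at 52 weeks + 5 days, window ±1 day.
- Nominal day: 52 × 7 + 5 = 369.
- Latest in-window day: 369 + 1 = 370.

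The period ends at the earliest of three events, one of which is visit 7. For a child still being dosed, the limit of 14 days after last administration cannot push the end beyond visit 7.

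**2. Day of the PPQ.** Week 56 is day 56 × 7 = 392, counting weeks from baseline as for the scheduled visits. Gap: 392 − 370 = 22 days after the latest in-window visit 7.

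**3. Dependence on the visit window.** There is none. Only children who switched complete the PPQ, and the switch happens at visit 7. Even if visit 7 is late, or week 56 is meant as four weeks after the switch, the response comes after the event that closes the period.

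**4. Other exploratory endpoints.** TB-CGHD-O, TB-CGHD-P, G-DAT and TRIM-CGHD-O are assessed at week 26, week 52 or both, so they fit the period. The PPQ is the only exploratory endpoint affected.

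**5. Children affected.** Norditropin arm under 2:1 randomisation: 192 / 3 = 64. Section 10.1 expects 10% to discontinue treatment or lack landmark data: 64 × 0.90 = 57.6, about 58. Section 9.1.5 and Appendix 9 also take eight countries out of the patient-reported part (Estonia, Hungary, Ireland, Latvia, Norway, Poland, Serbia, Spain). The documents do not give enrolment by country, so the figure cannot be narrowed further.

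**6. Extension endpoints.** (3 safety + 2 pharmacodynamic) × 4 time frames = 20 endpoint/time-frame pairs, counting HOMA once. Of these, 5 × 3 = 15 fall after week 52. Earliest in-window days (±7 days), compared with day 370:

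| Week | Earliest day | Days after day 370 |
|---|---|---|
| 104 | 104 × 7 − 7 = 721 | 351 |
| 156 | 156 × 7 − 7 = 1085 | 715 |
| 208 | 208 × 7 − 7 = 1449 | 1079 |

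All lie outside the three periods. However, Section 10.3.2 applies those periods only to the week-52 changes that it lists. For these 15 pairs an analysis is missing; no rule sends their data into a period that excludes them.

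**The case against.** The strongest reply is that the three periods were plainly written for the main phase. Section 10.2 sets them beside exclusions to be settled before the 52-week lock, Section 10.3.4 describes that lock separately, and a cutoff at visit 7 properly keeps post-switch data out of the randomised comparison. This stands as a reading of intent, and the cutoff itself is not an error. It does not rescue the PPQ, because Section 10.3.3 applies a main-phase period to a post-switch endpoint by name of the period.

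A second reply is that no sensible analyst would report an empty table when the same paragraph plans PPQ statistics. That is probably true, and it limits the practical harm. It still leaves the replacement rule unwritten.

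A third is that Section 10.3 allows a separate, more detailed SAP. It is optional and none is among the documents. It would be a suitable place for the correction.

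Three stronger readings are tempting, and the documents do not support them:
- A reader might infer that a stated rule also excludes the week 104 to 208 endpoints. As step 6 shows, that is an omission.
- A reader might infer that extension adverse events have no analysis. Section 10.3.5 plans tables for them, and Section 5.1 and the flowchart identify the extension. Only the period's boundaries are unstated.
- A reader might infer that summaries labelled as on somapacitan will mix children with three and four years of exposure. No section plans such a pooled summary.

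**Conclusion.** The point holds for the PPQ. Read together, Sections 10.2 and 10.3.3 exclude every on-schedule response from the analysis that Section 10.3.3 itself plans. The result rests on reading the period definitions literally and on the switch taking place at visit 7; it does not depend on the visit window or the drop-out rate. The 64 children are an upper bound on switchers, not an expected loss.

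For the extension, the conclusion is narrower: 15 of the 20 named safety and pharmacodynamic endpoint/time-frame pairs have no stated analysis, and the period for the planned adverse event tables is undefined.

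The consequences are limited. The PPQ is exploratory and descriptive, and the extension endpoints are supportive and single-arm. The primary endpoint, its type I error and all week-52 comparisons are unaffected.

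**What to change.** Make one edit across Sections 10.2, 10.3.2, 10.3.3 and 10.3.5, preferably before the interim database lock:

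- State that the three existing observation periods apply to the main phase only.
- Add an extension on-treatment period. It starts at visit 7, with no gap after the main period, and ends at the earliest of last trial contact, visit 19 or 14 days after last administration.
- In Section 10.3.3, assign the PPQ to this extension period and keep the other exploratory endpoints where they are.
- In Section 10.3.2, state that the week 104, 156 and 208 safety and pharmacodynamic endpoints of Sections 4.3.2.4 and 4.3.2.5 are summarised descriptively over the extension period.
- In Section 10.3.5, refer the extension adverse event tables to the same period.

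The cost is protocol or SAP wording and some descriptive table programming. No new data, visits or change to any week-52 analysis is needed.

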10.3 Statistical analyses

If necessary, a statistical analysis plan (SAP) may be written in addition to the protocol, including a more technical and detailed elaboration of the statistical analyses. The SAP will be finalised before database lock.

The one-sided test used for the primary endpoint is based on an alpha level of 2.5%. All other statistical tests conducted will be two-sided on the 5% significance level. Age group is defined as a factor with 2 levels: < 6 years, >= 6 years. Region and GH peak group, respectively, used as factors in the analysis models are defined identically to the stratification variables region and growth hormone peak level, respectively. All effect endpoints will be analysed using FAS and all safety endpoints will be analysed using SAS. The primary endpoint will additionally be analysed using PP as a support to the results achieved using FAS under the hypothetical strategy.

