9.4 Safety assessments

Planned time points for all safety assessments are provided in the flowchart Section 2.

A **concomitant illness** is any illness that is present at the start of the trial (i.e. at the first visit) or found as a result of a screening procedure or other trial procedures performed before exposure to trial product.

Medical history is a medical event that the subject has experienced in the past.

In case of an abnormal and clinically significant finding, the investigator must record the finding on the Medical History/Concomitant Illness form if it is present at screening. Any new finding fulfilling the AE definition (see Appendix 4) during the trial and any clinically significant worsening from baseline (Visit 2) must be reported as an AE (see Section 9.2).

GHD history

- Type of GH stimulation tests and result of peak GH values

- Standing height measured minimum 6 and maximum 18 months prior to screening. Standing height should be reported in centimetres with one decimal to the nearest 1 mm or in inches with one decimal. The pre-trial height assessment is collected to be used when evaluating inclusion criterion 5 and for baseline HV derivation.
- Parental height: Standing height for both biological parents in centimetres with one decimal to the nearest 1 mm or in inches with one decimal.

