10.1 Sample size determination

The sample size calculation is based on the primary estimand described in Section [4.2](#).

It is expected based on phase 2 trial data (NN8640-4172) that the proportion of subjects with no landmark visit data or who discontinued randomised treatment before landmark visit is 10% with similar withdrawal reasons in the two treatment arms (5% discontinuing randomised treatment but have landmark visit data and 5% withdrawn /lost to follow up with no landmark visit data). It is expected that subjects discontinuing their randomised treatment will start on ancillary treatment, if no medical reasons prohibits this. The term “retrieved subjects” will be used in this section as a short form for “subjects discontinuing randomised treatment but have landmark visit data”.

Assuming the same proportions of subjects with no landmark visit and retrieved subjects in the two arms leads to the following sample size calculation.

Primary estimand (FDA and PMDA)

The sample size is determined using a non-inferiority margin of 1.8 cm/year and a one sided two-group t-test with a significance level of 2.5% for a 2:1 randomisation ratio between somapacitan and Norditropin®.

As trial results from trials allowing ancillary therapy or having retrieved landmark data included in the analysis are limited, a conservative standard deviation for HV at week 52 was chosen (SD=3.5cm/year) and the different scenarios giving 90% power for the primary analysis are presented in the table below under the assumption of a true difference in annualized HV of 0 cm/year between the two treatment arms and no true difference in annualized HV between retrieved subjects and subjects staying on randomised treatment at landmark visit.

Table 3 Sample size for various standard deviations

SD	3.0 cm/year	3.25 cm/year	3.5 cm/year	3.75 cm/year
Primary estimand	144	171	192	219
(Treatment policy strategy)				

The SD candidates are based on reported SD values from clinical trials [21-23](#). For sensitivity analysis a tipping point analysis is planned and based on a penalty for imputed values in the somapacitan arm of 1.8 cm/year this gives a power of 87% (adjusted treatment effect: $0.9*0 - 0.05*1.8 = -0.09$), under the assumption of 5% of subjects not having landmark visit data (corresponding to an analysis that performs an imputation under the non-inferiority null method).²⁴

Primary estimand (EMA)

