10.3.1 Primary endpoint

The primary endpoint:

- Height velocity (cm/year) during the first 52 weeks will be derived from height measurements taken at baseline and the week 52 visit (landmark visit) in the following way: $HV = (\text{height at 52 weeks visit} - \text{height at baseline}) / (\text{time from baseline to 52 weeks visit in years})$.

Annualized HV at the intermediate visits: Week 13, 26 and 39, will be derived analogously to the week 52 HV: $HV = (\text{height at } j \text{ weeks visit} - \text{height at baseline}) / (\text{time from baseline to } j \text{ weeks visit in years})$, $j=13, 26, 39$.

Primary estimand (FDA and PMDA)

The primary objective is to compare the effect of somapacitan vs Norditropin® on longitudinal growth in children with GHD and the primary analysis of the primary endpoint will be used for confirming non-inferiority of somapacitan compared to Norditropin® based on the primary estimand Section [4.2.1](#)

The primary analysis of the primary endpoint is based on the FAS. Subjects with no landmark visit data will have landmark visit data imputed based on available landmark visit data from retrieved subjects from the same treatment arm using Multiple Imputations (MI). If number of retrieved subjects per arm is less than 20 for at least one of the treatment arms (based on the assumptions: ~6 from the largest treatment arm), MI will be done in a model using all landmark visit data from the same treatment arm but with different mean parameters for the two status subgroups: (stayed on randomised treatment at the landmark visit; combined group of withdrawals and retrieved subjects), but same variance.

The analysis will be implemented as follows:

In the first step, missing week 52 values are imputed using a Markov Chain Monte Carlo method. This imputation is done for each treatment group separately and 100 copies of the dataset will be generated (seed=5297). The number of copies can be increased if the estimation process does not result in robust estimates.

For each of the complete data sets, HV at week 52 is analysed using an analysis of covariance model with treatment, gender, age group, region, GH peak group and gender by age group by region interaction term as factors, and baseline height as covariate.

The estimates and standard deviations for the 100 data sets are pooled to one estimate and associated standard deviation using Rubin's formula:

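### Baseline height velocity and continuous GH peak are collected but left out of both primary models; adding them would be a cheap, modest gain in precision

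*Combined protocol and SAP*

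**What the plan says.** Section 10.3 defines age for the models: "Age group is defined as a factor with 2 levels: < 6 years, >= 6 years". It defines region and GH peak group as the stratification variables, so GH peak enters as below 7.0 versus 7.0 ng/ml or above (section 7.3).

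In section 10.3.1 the ANCOVA for the treatment policy estimand has treatment, gender, age group, region, "GH peak group and gender by age group by region interaction term as factors, and baseline height as covariate". The MMRM for the hypothetical estimand uses the same baseline terms, nested within week. Neither contains baseline HV.

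The finer data are collected. Section 9.4 (GHD history) lists "Type of GH stimulation tests and result of peak GH values" and states: "The pre-trial height assessment is collected to be used when evaluating inclusion criterion 5 and for baseline HV derivation". Inclusion criterion 5 requires a pre-trial HV for every child. Section 10.3.2 already uses baseline HV SDS as a covariate when analysing change in HV SDS.

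Appendix 9 sets the Japanese eligibility ceiling for peak GH at 6 ng/ml.

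**The concern.** Baseline values that predict the outcome, if pre-specified, reduce the standard error of a randomised comparison. Two plausible predictors of first-year growth are underused. Baseline HV, the pre-treatment value of the endpoint itself, is absent. GH peak, a marker of how severe the deficiency is, is reduced to two groups. The cut does no work in Japan: every eligible Japanese child is at or below 6 ng/ml, so the factor is constant within one of the two region strata.

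The secondary HV SDS model adjusts for baseline HV SDS while the primary HV models have no counterpart.

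What is at stake is the width of the confidence interval that decides non-inferiority and, since version 7.0, superiority. Validity is not at stake.

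**Working it through.** **Inputs.** Section 10.1: "The sample size is determined using a non-inferiority margin of 1.8 cm/year"; "one sided two-group t-test with a significance level of 2.5% for a 2:1 randomisation ratio"; SD 3.5 cm/year; true difference 0; 5% without landmark data. N = 192, that is 128 + 64.

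**The plan's own figure.** With noncentral-t power, the smallest 2:1 total reaching 90% is 183, and 183 / 0.95 = 192.6, against the stated 192. At N = 192 with 5% lost (121.6 and 60.8), SE = 3.5 × √(1/121.6 + 1/60.8) = 0.550, noncentrality = 1.8 / 0.550 = 3.27, and power = 90.3%. With 10% lost, as for the hypothetical estimand, power is 88.7% (stated 88%). The sizing reproduces and uses no covariates.

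**Effect of added covariates.** Let r² be the share of the variance left by the planned model that the additions explain. The SE is multiplied by √(1 − r²). The documents give no value, so r² is an assumption. The table starts from SD 3.5, as if the planned terms explained nothing, so its non-inferiority power gains are upper-end figures for each r². The last row takes the phase 2 difference in HV (11.5 − 9.8 = 1.7 cm/year, version 7.0 rationale) as true.

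| r² | 0 | 2% | 5% | 10% |
|---|---|---|---|---|
| Fall in SE | – | 1.0% | 2.5% | 5.1% |
| 95% CI half-width, N = 192, cm/year | 1.06 | 1.05 | 1.03 | 1.00 |
| Non-inferiority power, 5% lost | 90.3% | 90.8% | 91.6% | 93.0% |
| Non-inferiority power, 10% lost | 88.7% | 89.3% | 90.2% | 91.6% |
| Superiority power at 1.7 cm/year, 5% lost | 86.8% | 87.4% | 88.4% | 90.0% |

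**A more realistic start.** If the planned terms already explain 10%, the SD is 3.5 × √0.90 = 3.32 and power is 93.0% before any change. A further 5% gives 3.5 × √(0.90 × 0.95) = 3.24 and 94.1%, a gain of 1.1 points. If they explain 20%, power goes from 95.4% to 96.2%, a gain of 0.8 points.

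**Baseline HV alone.** Section 5.4 cites an SD of baseline HV of 1.09 cm/year in a GHD trial. The variance explained is (slope × 1.09 / 3.5)². Assumed slopes of 0.25, 0.5 and 1.0 give 0.6%, 2.4% and 9.7%, before any overlap with planned terms.

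**Which variable matters.** In a simulation with assumed correlations with week-52 HV (age 0.3–0.5, GH peak 0.2–0.4, baseline HV 0–0.3), adding all three to the planned terms cut residual variance by a further 2% to 26%. Continuous age alone cut it by 0.4% to 4.7%, because baseline height is already a continuous covariate and tracks age.

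**The case against.** The strongest reply is that nothing is broken. Both models adjust for all four stratification factors and for continuous baseline height. The sample size rests on an unadjusted t-test with an SD the sponsor calls conservative, so 90% power is met without covariate credit. That stands.

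The candidate covariates are also imperfect. Baseline HV is restricted by eligibility (below the 25th percentile), rests on a height taken 6 to 18 months before screening outside the trial's measurement procedure, and describes untreated growth. GH peak comes from different stimulation tests, with similar local standards allowed and a separate Japanese definition. These limits stand too: they can shrink the gain to near zero. They do not bias a randomised comparison.

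A reader might infer more than the documents support:

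- That power is near its floor. The 90.3% is the power of the unadjusted t-test, not of the planned ANCOVA, which is higher if its terms are prognostic.
- That splitting age at 6 keeps only 73–75% of the age information, or splitting GH peak at 7 only 63%. Both figures assume evenly spread values, which the documents do not show. The age figure also ignores baseline height.
- That a SAP edit is enough. The models are in protocol section 10.3.1, and section 10.3 makes a SAP optional.

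**Conclusion.** The point holds as an efficiency recommendation. The primary models leave out baseline HV and reduce GH peak to two levels that do not vary among eligible Japanese children, although the finer values are already collected.

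The size cannot be read from the documents. On assumed shares of 2% to 10% of the remaining variance, the SE falls by about 1% to 5% and non-inferiority power rises by at most 0.5 to 2.7 points. The rise is smaller if the planned terms already explain variance, and nil if the additions are not prognostic beyond them. The practical benefit is mainly a narrower interval, most useful for the superiority test. The case rests on GH peak and baseline HV; continuous age adds little.

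**What to change.** Amend protocol section 10.3.1, and any SAP, before the interim database lock, while the sponsor staff who interpret data are still blinded (section 7.4).

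- Keep the stratification factors, the interaction and baseline height.
- Add baseline HV, derived as in section 10.3.2, and log GH peak as pre-specified covariates in the ANCOVA. In the MMRM, nest them within week.
- Define one peak value per child, for example the highest across that child's tests.
- Treat continuous age at randomisation as optional. Germany, Hungary, Spain and Switzerland record year of birth only.
- State whether the additions carry over to section 10.3.2, whose height SDS and HV SDS models are defined by reference to the primary model. Otherwise baseline HV and baseline HV SDS would sit in the same model.

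The cost is a protocol change to the primary model, plus two parameters in the ANCOVA and eight in the MMRM (two covariates by four visits). No new visit, sample or child is needed.
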